**Analysis for Aim 1B:** Two ActiGraph-derived measures, total sleep time (TSTact) and sleep efficiency (SEact), will serve as outcomes in separate mixed-effects models with fixed effects for time and day (within the ActiGraph epoch) and subject-specific random intercepts, assuming an AR(1) correlation structure. We will assess whether adjustment for weekday/weekend is warranted. Subject-specific means of these measures will be used as predictors of their subjective

counterparts (TSTact, SEact) in additional mixed models testing for treatment group differences in the association between objective and subjective sleep measures. Moderation by trauma history and attachment will be explored.

**Aim 2. Determine the maintenance of improved maternal mood and differences in infant behavior.** We hypothesize that PREPP will be associated with: (A) Lower rates of PPD and distress, including poor sleep efficiency, assessed by interviewer-rated and self-report questionnaires as well as sleep actigraphy. (B) Less infant fuss/cry behavior and longer nocturnal sleep bouts based on maternal report and actigraphy.

**Analysis for Aim 2A:** Separate linear mixed-effects models will be used for each maternal mood outcome (PHQ-9, HRSD, EPDS, HRSA, PSQI) and ActiGraph-derived sleep measures. Models will include Treatment, Time (6, 12, and 16 weeks postpartum), and their interaction, with baseline (pregnancy) values as covariates. Subject-specific random intercepts will be included. The primary parameter of interest is the Treatment  $\times$  Time interaction; if non-significant, the main effect of Treatment will be tested. PPD diagnosis will be modeled using mixed-effects logistic regression with analogous fixed effects.

For infant outcomes (6 and 16 weeks), linear mixed-effects models will assess Treatment effects without Time  $\times$  Treatment interaction. Sleep data will be processed as in Aim 1B. Covariates include time-varying factors such as weaning, solid food introduction, maternal return to work, and social support. Moderators (infant sex, trauma history, attachment) will also be assessed.

**Analysis for Aim 2B:** Infant sleep and cry behavior at 6 and 16 weeks will be compared using mixed-effects models with Treatment, Time, and their interaction as fixed effects. Covariates and secondary analyses will be same as those in Aim 2A.

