**Power analysis** We adjusted for multiple comparisons (five primary outcomes across Aims 1 and 2) using Bonferroni correction, resulting in a significance threshold of 0.01. For Aim 1, with  $N = 214$  and an assumed 5% attrition, our mixed-effects model analysis is powered to detect a minimum effect size of  $d = 0.48$  (assuming within-subject correlation  $r = 0.2$ ). Prior research has shown larger effects (e.g.,  $d = 0.85$  for EPDS in mindfulness-based therapy), indicating our design has ample power. For Aim 2, assuming 33% attrition and five primary outcomes, power calculations show that  $N = 107$  per group is sufficient to detect interactions as small as  $d = 0.087$  with 80% power at a Bonferroni-adjusted  $\alpha = 0.01$ . Our preliminary data support this assumption. For Aim 3, based on tabulated recommendations 184 for sample sizes needed to test mediation effects, with  $N=142$  completers (assuming 33% attrition for assessments), we have more than 80% power to detect a significant mediation effect with moderate effect sizes ( $d=0.54$ ,

$r=0.26$  of both paths (i.e. the paths from treatment to the mediator(s) and the mediator(s) to outcomes). Since the full sample ( $N = 214$ ) will be used in mediation models, the actual power will exceed this estimate.

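### Aim 2A makes Treatment × Time over three postpartum visits primary but names only a random intercept, so the interaction test is too liberal if correlation falls with time between visits

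*Combined protocol and SAP*

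**What the plan says.** The Statistical Analysis Plan, Analysis for Aim 2A, sets out the maternal models: "Separate linear mixed-effects models will be used for each maternal mood outcome (PHQ-9, HRSD, EPDS, HRSA, PSQI") and the ActiGraph sleep measures. The fixed effects are Treatment, "Time (6, 12, and 16 weeks postpartum), and their interaction, with baseline (pregnancy) values as covariates". On correlation and on the target of inference it says "Subject-specific random intercepts will be included. The primary parameter of interest is the Treatment" × Time interaction (the quote stops before the symbol). A sequential rule follows: "if non-significant, the main effect of Treatment will be tested".

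The instrument table shows that all five scales are collected at 6, 12 and 16 weeks, so each model has three postpartum visits.

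For these scores the SAP names no random slope, residual correlation structure, unstructured covariance, robust standard error or degrees-of-freedom method. A serial structure does appear under Aim 1B, for the ActiGraph measures: "subject-specific random intercepts, assuming an AR(1) correlation structure". The later cross-reference to Aim 1B is in the infant-outcome paragraph and concerns sleep data. The SAP does not say whether Time is a three-level factor or a linear term in weeks.

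**The concern.** A random intercept with independent residuals lets women differ in level but not in course. It forces the 6–12, 12–16 and 6–16 week correlations to be equal, and the variances too. Treatment × Time compares courses, and the random intercept cancels from every within-woman contrast. The standard error of the declared primary parameter therefore rests wholly on the part of the covariance that the model fixes by assumption.

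If correlation falls as visits move apart, that standard error is too small for the long contrast. Two features of this plan raise the stakes. The threshold comes from a multiplicity correction ("using Bonferroni correction, resulting in a significance threshold of 0.01"), and an inflated level gives some of that protection back. In addition, a false-positive interaction means that the Treatment main effect is not tested under the stated sequence.

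The point concerns the three-visit scale scores, not the daily actigraphy or the logistic model for PPD diagnosis.

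**Working it through.** **The plan's own figure.** The power analysis gives d = 0.087 as the smallest detectable Aim 2 interaction. With a two-sided 0.01 test (sidedness is not stated) and 80% power, z = 2.576 + 0.842 ≈ 3.417. A slope difference under equal correlation is detectable at d = 3.417·√[2(1−r)/(Sxx·n)]. Using weeks 6, 12 and 16, Sxx = 50.67; with n = 72 this gives 0.072 at r = 0.2 and 0.080 at r = 0. So 0.087 is not reproduced from the documented inputs. That is a separate matter, and it supplies no Aim 2 correlation.

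**Inputs.**
- From the SAP: visits at weeks 6, 12 and 16; level 0.01; 142 completers, so 71 per arm (107 × 0.67 = 71.7).
- Assumed: complete data, equal variances, and the visit-to-visit correlations below, read as residual correlations after the model's covariates. The only correlation in the SAP is r = 0.2, given for Aim 1.

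**Linear Time (1 df).** The centred weeks are c = (−5.33, 0.67, 4.67), and c′c = 50.67. Let R be the true correlation matrix. The random-intercept model uses a contrast variance of 1 − ρ̄, where ρ̄ is the mean of the three correlations. The true value is c′Rc/c′c. Hence

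SE ratio = √[(1 − ρ̄)/(c′Rc/c′c)], and actual level ≈ 2[1 − Φ(2.576 × SE ratio)].

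Example, 0.6/0.6/0.5: 1 − ρ̄ = 0.433. c′Rc/c′c = 1 + 2[0.6(−3.56) + 0.6(3.11) + 0.5(−24.89)]/50.67 = 0.498. SE ratio = √(0.433/0.498) = 0.933. Level = 2[1 − Φ(2.402)] = 0.016.

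**Categorical Time (2 df).** The level was simulated under the null with 71 per arm. With complete data the random-intercept test is the split-plot F test.

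| Correlations 6–12 / 12–16 / 6–16 | 1 − ρ̄ | c′Rc/c′c | SE ratio, linear | Level, linear | Level, categorical |
|---|---|---|---|---|---|
| 0.6 / 0.6 / 0.5 | 0.433 | 0.498 | 0.933 | 0.016 | 0.010–0.011 |
| 0.6 / 0.7 / 0.5 | 0.400 | 0.511 | 0.885 | 0.023 | 0.012 |
| 0.7 / 0.7 / 0.5 | 0.367 | 0.496 | 0.859 | 0.027 | 0.014 |
| 0.6 / 0.7 / 0.4 | 0.433 | 0.609 | 0.844 | 0.030 | 0.015 |
| 0.7 / 0.7 / 0.4 | 0.400 | 0.595 | 0.820 | 0.035 | 0.017 |
| 0.2 / 0.2 / 0.1 | 0.833 | 0.898 | 0.963 | 0.013 | 0.010 |
| equal (0.2 or 0.5) | – | – | 1.000 | 0.010 | 0.010 |

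The linear column is the formula. Simulation agrees to within about 0.001 and reaches 0.036 in the worst row and 0.014 in the 0.2/0.2/0.1 row.

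**Differences between specific visits.** For a pair with true correlation ρ, the SE ratio is √[(1 − ρ̄)/(1 − ρ)]. Under 0.6/0.7/0.4, the 6-to-16-week difference gives √(0.433/0.6) = 0.85, so its standard error is 15% too small. The 12-to-16-week difference gives √(0.433/0.3) = 1.20, so its standard error is 20% too large. The coding of Time does not alter this.

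**After the fix.** With an unstructured covariance over the three visits, the simulated level at nominal 0.01 is 0.0095–0.0104 in every pattern tried.

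**The case against.** Four arguments can be made in the plan's defence.

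1. **Three listed visits are naturally a factor.** On that reading the level is at most about 0.017 over the assumed range and hardly above 0.010 when the fall is mild. This stands and limits the size. The coding is not stated, however, so the linear reading is not excluded.

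2. **The only documented correlation is low.** At 0.2/0.2/0.1 the inflation is small. This stands as a case to show, but r = 0.2 is given for Aim 1 and not for the postpartum visits.

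3. **The baseline covariate lowers the residual correlations.** It does, but that alone does not reduce the inflation. A component shared equally by all three visits cancels from the contrasts. Removing 0.4 from every entry of 0.6/0.6/0.5 leaves variance 0.6 and covariances 0.2/0.2/0.1. The model's contrast variance is still 0.6 − 0.167 = 0.433 and the true one still 0.498, so the ratio is still 0.933.

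4. **Random-intercept models for three visits are common.** True, and the test holds its level if the correlations are equal.

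A reader might go further and infer that all five scales are in fact tested above 0.01. The documents do not support that, because nothing in them shows that correlation falls. A reader might also infer that the SAP forbids any other structure; it names only the random intercept and excludes nothing. Finally, incomplete visits may be handled less well under a wrong covariance, since up to 33% attrition is expected and likelihood estimates then depend on it. The calculations here use complete data and do not measure that effect.

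**Conclusion.** The concern holds conditionally. As written, the working covariance for the Aim 2A scale scores is equal variance and equal correlation, and the primary parameter is the one most exposed to that assumption. If correlation falls with the gap between visits, the interaction test is too liberal. Over the main assumed range, the nominal 0.01 test runs at about 0.010–0.017 with categorical Time. With linear Time it runs at about 0.016–0.036, with a standard error about 7–18% too small. Standard errors for differences between particular visits are then wrong under either coding. With equal correlations there is no inflation.

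The direction is secure. The size depends on correlations that the documents do not give and on a coding of Time that they leave open. The matter is worth correcting before analysis but does not invalidate the design.

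**What to change.** In the Aim 2A analysis, for the three-visit scale scores, state that Time is categorical and that the model uses an unstructured within-woman covariance in place of the random intercept, with Kenward-Roger degrees of freedom. If Time is to be linear in weeks, say so and add a subject-specific random slope.

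The cost is one SAP sentence and no new data. The unstructured covariance has six parameters (three variances and three correlations), which about 142 women can support. The price is a few more covariance parameters and a slightly wider interval.

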#### **Statistical Analysis Plan**

**Overall.** Based on preliminary data, we anticipate minimal attrition ( $\leq 5\%$ ) during the first two assessment sessions (pre-delivery), and up to 33% attrition postpartum across both groups in the worst-case scenario. All participants with data available for a given study phase (pre- or postpartum) will be included in the primary analyses. Before conducting hypothesis tests, we will screen all variables at all time points for out-of-range values, outliers, and data inconsistencies. Means, standard deviations, interquartile range, minima, and maxima for continuous variables and proportions for categorical variables will be reported.

Following CONSORT guidelines, the primary analyses for all aims will follow an intention-to-treat (ITT) approach, including all randomized participants regardless of treatment adherence or dropout. If significant imbalances in baseline covariates (e.g., maternal age, BMI, birth order, infant sex) are observed despite randomization, these variables will be included as covariates in the models. Additional exploratory models will examine relevant biological factors, such as maternal BMI, fetal/infant sex, maternal age, infant gestational age at birth, and birthweight corrected for birth age, as potential covariates.

**Aim 1.** Reduce women's distress during pregnancy. We hypothesize that PREPP will be associated with: (A) Diminished depressive symptoms using interviewer-rated and self-report questionnaires; (B) Improved perception of sleep quality relative to objective changes in sleep duration (per self report and actigraphy).

**Analysis for Aim 1A:** For depressive symptom outcomes (HRSD, PHQ-9, HRSA, PSQI, EPDS), we will fit linear mixed-effects models with fixed effects for Treatment (PREPP vs. ETau), Time (2nd and 3rd assessments), and birth order, along with subject-specific random intercepts. For EPDS, we will adjust for the screening score and test a Treatment  $\times$  Screening Score interaction as a secondary analysis. Additional moderators will also be tested.

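### Aim 2A's primary test asks whether the arm difference changes between postpartum visits, while hypothesis (A) is about a lower level; if that test is significant, no level contrast is named

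*Combined protocol and SAP*

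**What the plan says.** All references are to the Statistical Analysis Plan in the combined protocol and SAP.

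- Aim 2 is headed "Determine the maintenance of improved maternal mood". Its hypothesis (A) is "Lower rates of PPD and distress, including poor sleep efficiency, assessed by interviewer-rated and self-report questionnaires", with actigraphy added.
- Analysis for Aim 2A: "Separate linear mixed-effects models will be used for each maternal mood outcome (PHQ-9, HRSD, EPDS, HRSA, PSQI") and for the ActiGraph sleep measures. "Models will include Treatment, Time (6, 12, and 16 weeks postpartum), and their interaction, with baseline (pregnancy) values as covariates". Treatment × Time is called the primary parameter, with the rule "Time interaction; if non-significant, the main effect of Treatment will be tested". For diagnosis, "PPD diagnosis will be modeled using mixed-effects logistic regression with analogous fixed effects".
- Analysis for Aim 1A covers the same five scales, "For depressive symptom outcomes (HRSD, PHQ-9, HRSA, PSQI, EPDS"), with Treatment and Time but no interaction between them. That is a direct test of level.
- Power analysis: "We adjusted for multiple comparisons (five primary outcomes across Aims 1 and 2) using Bonferroni correction, resulting in a significance threshold of 0.01". The five outcomes are not named there. Aim 2 power is given for interactions only.

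**The concern.** Pregnancy values enter as covariates, and Time has only postpartum levels. Treatment × Time is therefore zero whenever the arm difference is the same at 6, 12 and 16 weeks, whether that difference is large or nil. It bears on maintenance, but it does not test whether PREPP mothers have lower scores.

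The level is tested only on the non-significant branch. On the significant branch the plan names no contrast, either averaged or by visit. A fading benefit, a growing one and a reversal with no average benefit would all end as a significant primary result, with hypothesis (A) untested. Any contrast run afterwards would be chosen after seeing the data.

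The rule also gives each outcome two routes to significance, while the divisor of five counts outcomes and not tests.

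**Working it through.** **Inputs from the plan.** 107 per group; 33% postpartum attrition, its worst case; threshold 0.01. This gives 107 × 0.67 = 71.7 per group.

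**Assumptions.** Compound symmetry, with r shown as a range because r = 0.2 is stated only for Aim 1. Time is categorical (2 df), which the plan does not say. Tests are two-sided. The main effect is the average over the three visits. Both steps use 0.01, the only threshold given. No gain from baseline adjustment is counted.

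**The plan's own figure.** 0.05/5 = 0.01, which reproduces.

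**Constant benefit.** For d = 0.48, the plan's detectable effect for Aim 1, the interaction rejects at its alpha, 1%. The averaged contrast has SE = √[(2/71.7)(1 + 2r)/3] = 0.114 / 0.136 / 0.149 at r = 0.2 / 0.5 / 0.7. Two-step power is 94% / 82% / 73%, the same as a direct level test.

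**Changing benefit.** The interaction has noncentrality λ = (71.7/2) × Σ(δₜ − δ̄)²/(1 − r), tested by F on 2 and 283 df at 0.01. Effects are in SD, positive meaning benefit.

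| Effect at 6 / 12 / 16 weeks | Σ(δₜ − δ̄)² | λ at r = 0.2 / 0.5 | Interaction significant, so no level test |
|---|---|---|---|
| 0.8 / 0.4 / 0 | 0.32 | 14.3 / 22.9 | 81% / 97% |
| −0.4 / 0 / +0.4 (average zero) | 0.32 | 14.3 / 22.9 | 81% / 97% |
| 0.6 / 0.3 / 0 | 0.18 | 8.1 / 12.9 | 48% / 75% |
| 0.8 / 0.6 / 0.4 | 0.08 | 3.6 / 5.7 | 17% / 32% |
| 0.6 / 0.45 / 0.3 | 0.045 | 2.0 / 3.2 | 8% / 15% |
| 0.5 / 0.4 / 0.3 | 0.02 | 0.9 / 1.4 | 4% / 6% |

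The first two rows are upper-end cases: a complete fade and a sign reversal. The proportions rise with r.

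**Type I error with no effect.** Per outcome, 1 − 0.99² = 0.0199, against 0.01 for a single test. For five independent scales, 1 − 0.99¹⁰ = 0.096, against 1 − 0.99⁵ = 0.049. Correlated scales were simulated:

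| Between-scale correlation | Two-step, any of five | One test each |
|---|---|---|
| 0 | 9.6% | 4.9% |
| 0.5 | 8.3% | 4.2% |
| 0.7 | 7.0% | 3.5% |
| 0.9 | about 4.7% | 2.3% |

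If only two of the five primary outcomes belong to Aim 2A, the two-step figure is 3.0–3.9%. With three, it is 5.8% if independent and 4.8% at correlation 0.7.

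**Detectable level effect, which the plan does not give.** At 0.01 and 80% power, (2.576 + 0.842) × SE = 0.39 / 0.47 / 0.51 at r = 0.2 / 0.5 / 0.7.

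**The case against.** Testing the interaction and then the main effect is a common sequence, and the interaction does speak to the maintenance named in the aim's heading. One sentence specifying per-visit contrasts after a significant interaction would close the gap in the text. That has weight, but it would leave two routes to significance per outcome, and the primary parameter would still not be the one that hypothesis (A) states.

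A reader might infer more than the documents support:

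- *That the plan would miss a sustained benefit.* It would not, because the fallback tests level at full power.
- *That error exceeds 5% on every reading.* The primary outcomes are unnamed and the second step has no stated alpha. With fewer Aim 2A outcomes, or highly correlated scales, the rate can stay below 5%.
- *That the level test is usually skipped.* That holds for steep fades to zero. At r = 0.2–0.5, the partial fades shown reach it in most trials.
- *That the baseline covariate is measured after randomisation.* The plan does not say so. The Baseline Assessment at 20–29 weeks precedes randomisation at Prenatal Session 1. Only the word pregnancy needs tightening, chiefly for PHQ-9 and PSQI, which the instrument table first lists at that session.

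**Conclusion.** Wrong as written. The primary parameter in Aim 2A does not test the level claim in hypothesis (A), and a significant primary result neither shows benefit nor leads to a planned test of it. This part follows from the text alone.

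The practical size depends on the course of the effect: no loss under a constant benefit, 4–32% of trials without a level test under the partial fades shown, and 48–97% under full fades. These figures rest on 71.7 per group, categorical Time, compound symmetry and r of 0.2 to 0.5.

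If both steps use 0.01, error per outcome roughly doubles to 2%. The overall excess above 5% is conditional: it arises if all five scales are primary in Aim 2A and their correlation is no more than about 0.7. The data remain usable, so this should be fixed before analysis but does not undermine the trial.

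**What to change.** For each Aim 2A maternal mood scale:

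1. Make one unconditional Treatment contrast primary at 0.01: the effect averaged over 6, 12 and 16 weeks, from the same mixed model, adjusted for the pre-randomisation value. For PHQ-9 and PSQI, state that the Prenatal Session 1 value is taken before allocation.
2. Drop the two-step rule. Report Treatment × Time and the per-visit contrasts, including week 16 for maintenance, as secondary.
3. Name the five primary outcomes, and say whether 0.01 controls error within each aim or across both. If the same five scales are primary in both aims and 5% is meant across them, there are ten tests: use 0.05/10 = 0.005, or Holm.
4. State Aim 2 power for the level contrast, using the detectable effects of 0.39 / 0.47 / 0.51 above.

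The cost is SAP wording. At 0.01 the averaged contrast loses no power against the present fallback. At 0.005 the detectable d rises by about 7%, to 0.42 / 0.50 / 0.55. One drawback remains: the averaged contrast can be significant when the benefit has gone by week 16 (81% of trials for 0.8 / 0.4 / 0 at r = 0.2). The per-visit contrasts must therefore be reported beside it.

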#### **Prenatal Session 1 (28-32 weeks gestation)**

At this time point, if the individual agrees to participate in this session and gives consent, the individual is randomly assigned to one of two groups: Intervention vs. Enhanced Treatment As Usual (ETAU). When the participants are 28-32 weeks pregnant, they participate in an in-person session (pre-COVID) or in a virtual session (during COVID), either by phone or video call, and are asked to complete mood assessments, a cognitive assessments and answer questionnaires about feelings, life events, and sleep. Participants are asked a questionnaire about the effect of COVID-19 on their lives. In total, these questionnaires take about 90 minutes. All questionnaire results are entered in Redcap, an online secure database. All information entered in REDCap is de-identified using a screen ID. At home, we ask participants to wear an activity monitor for 7 full 24-hour days. We ask participants to complete a sleep diary noting sleep times and durations for the seven consecutive days they are wearing the activity monitor.

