### List of Instruments and Standardized Protocols:

Data Collection Instrument	Screening (20-29 weeks)	Prenatal 1 (28-32 weeks)	Prenatal 2 (34-39 weeks)	Newborn	6 week	12 week	16 week
Demographics		X	X		X	X	X
Newborn Delivery Data				X			
Pregnancy Medical History	X						

Predictive Index of Postnatal Depression (PIPD)	X						
Mini International Neuropsychiatric Interview (MINI)	X						
Columbia Suicide Severity Rating Scale (C-SSRS)	X	X	X		X	X	X
Edinburgh Postnatal Depression Scale (EPDS)	X	X	X		X	X	X
Hamilton Anxiety Scale (HRSA)	X	X	X		X	X	X
Hamilton Depression Scale (HRSD)	X	X	X		X	X	X
Personal Health Questionnaire-9 (PHQ-9)		X	X		X	X	X
Pittsburgh Sleep Quality Index (PSQI)		X	X		X	X	X
Pregnancy Physical Activity Questionnaire (PPAQ)		X	X				
Family History Screen (FHS)				X			
Adverse Childhood Experiences Questionnaire (ACE)		X					
Benevolent Childhood Experiences scale (BCEs)		X					
The Hunger Vital Sign (HVS)		X	X		X		X
Experiences in Close Relationships (ECR)		X					
Childhood Trauma Questionnaire (CTQ)		X					
Multidimensional Scale of Perceived Social Support Questionnaire (MSPSS)		X			X		
Maternal Antenatal Attachment Scale (MAAS)			X				
Abbreviated Brief Infant Sleep Questionnaire (BISQ)					X		X
Childcare Arrangement Scale (CAS)					X		X
Infant Intentionality Questionnaire (IIQ)					X		X
Infant Nutrition Questionnaire (INQ)					X		X
Karitane Parenting Confidence Scale (KPCS)					X		X
Short Acculturation Scale for Hispanics (SASH)			X				
Experiences of Discrimination (EOD)			X				

Adult Attachment Questionnaire (AAQ)		X	X				
Maternal Postnatal Attachment Scale (MPAS)					X		X
Being a Mother (BaM-13)							X
Parental Bonding Instrument for Mothers (PBI-M)		X	X				
Parental Bonding Instrument for Fathers (PBI-F)		X	X				
Rejection Sensitivity Questionnaire (RSQ)		X					
Difficulties in Emotion Regulation Scale (DERS)		X	X		X		
Interpersonal Support Evaluation List (ISEL)		X					
COVID-19 Questionnaire		X					X
Utilization of PREPP Skills		X	X		X		X
Infant EEG				X	X		
Adult Activity Monitor		X	X		X		X
Sleep Log		X	X		X		X
Infant Smart Sleep Sensor					X		X
Baby Day Diary					X		X
Infant Care Routine, video					X		X
Modified 'double' Still Face Protocol, video (SFP)							X
Free Play, Video							X

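### The infant-outcome models adjust for covariates that arise after randomisation, and Aims 2A and 2B specify different models for the same visits

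*Combined protocol and SAP*

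**What the plan says.** At Prenatal Session 1 (28–32 weeks' gestation), "the individual is randomly assigned to one of two groups". The opening of the Statistical Analysis Plan commits the primary analyses of all aims to intention to treat and allows adjustment for baseline covariates found to be imbalanced. Further covariate models are described there as exploratory.

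The Analysis for Aim 2A turns to infant outcomes at 6 and 16 weeks: "linear mixed-effects models will assess Treatment effects without Time" × Treatment interaction. It then says: "Covariates include time-varying factors such as weaning, solid food introduction, maternal return to work, and social support". No sensitivity, secondary or exploratory label is attached.

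The Analysis for Aim 2B says that infant sleep and cry at 6 and 16 weeks "will be compared using mixed-effects models with Treatment, Time, and their interaction as fixed effects", and that "Covariates and secondary analyses will be same as those in Aim 2A". It names no parameter of interest. For maternal mood, by contrast, Aim 2A does: the interaction first, and the main effect if the interaction is not significant.

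**The concern.** There are two separate problems.

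- **Covariates.** An intention-to-treat comparison estimates the effect of being assigned to PREPP. If PREPP alters a covariate measured after assignment, adjusting for it can remove the part of the effect that runs through it. If the covariate and the outcome share an unmeasured cause, adjustment can also open a collider path.
- **Model conflict.** The two paragraphs give different models for overlapping outcomes at the same visits. One tests an average effect. The other contains a change in effect between visits and does not say which coefficient counts. The hypothesis on infant fuss/cry and nocturnal sleep therefore has no single defined test, and the choice could be made after seeing the data.

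**Working it through.** **1. When the covariates arise** (Prenatal Session 1; List of Instruments)

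| Covariate | Scheduled source | Relation to assignment |
|---|---|---|
| Weaning, solid foods | Infant Nutrition Questionnaire at 6 and 16 weeks (taken here as the feeding measure; its content is not shown) | After |
| Return to work | No instrument named for it | After, as a postpartum event |
| Social support | MSPSS at Prenatal 1 and 6 weeks; ISEL at Prenatal 1 only | Prenatal 1: order not stated; 6 weeks: after |

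Neither support scale is scheduled at 16 weeks, so support cannot be updated for the second infant visit. If it varies at all, it must use the 6-week MSPSS. The Prenatal 1 value is not clearly a baseline either: assignment takes place at that session, and Aim 1A models the second and third assessments as outcomes.

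**2. What adjustment can do.** Feeding is the most plausible route, because the PREPP arm description includes lengthening night-feeding intervals. The documents do not show that PREPP changes weaning or solid foods. The following path sizes, in units of about 1 SD, are assumptions for illustration only.

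- Pure mediator, direct effect 0.40, PREPP-to-covariate 0.3, covariate-to-outcome 0.3: the total effect is 0.40 + 0.3 × 0.3 = 0.49. The adjusted coefficient is 0.40.
- Covariate with no effect on the outcome but an unmeasured cause in common with it (0.5 on each), PREPP-to-covariate 0.3: a true effect of 0.40 becomes 0.325, and a true null becomes −0.074.
- PREPP does not change the covariate: no bias.

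**3. Check of the power convention.** The plan gives no power figure for infant outcomes. Its Aim 1 figure, d = 0.48, can be reproduced as a single-visit comparison with two-sided alpha 0.01 and 80% power: n = 107 × 0.95 = 101.65 per arm, and 3.417 × √(2/101.65) = 0.479. The same convention is used below.

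**4. What each infant model can detect.** Inputs from the Power analysis: 107 per arm, 33% attrition, alpha 0.01, 80% power. Then n = 107 × 0.67 = 71.7 per arm. The outcome SD is taken as 1 at each visit, with one value per visit. The correlation r between visits is an assumption: the plan gives r = 0.2 for Aim 1 only.

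Detectable effect = (2.576 + 0.842) × SD × √(2/71.7) = 3.417 × SD × 0.167 = 0.571 × SD, where:

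- two-visit average: SD = √((1 + r)/2)
- interaction (16-week minus 6-week difference): SD = √(2(1 − r))
- 6-week effect alone: SD = 1

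| r | Two-visit average | Interaction | 6-week effect alone |
|---|---|---|---|
| 0.2 | 0.44 | 0.72 | 0.57 |
| 0.5 | 0.49 | 0.57 | 0.57 |
| 0.7 | 0.53 | 0.44 | 0.57 |

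The last column is what the Treatment coefficient in the Aim 2B model measures if 6 weeks is the reference visit. At r = 0.2, a constant 0.44 SD effect at both visits has about 80% power on the average test and 1% (alpha itself) on the interaction test. At alpha 0.05 and r = 0.2 the detectable effects are 0.36 SD (average) and 0.59 SD (interaction).

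**5. If either test may be reported.** With equal variances at the two visits, the average and the difference are uncorrelated. The chance of at least one false positive per outcome is 1 − 0.99² = 0.0199 at alpha 0.01. Simulation with 400,000 draws gave 0.0201 at r = 0.2 and 0.0197 at r = 0.7. At alpha 0.05 it is 1 − 0.95² = 0.0975.

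**The case against.** The strongest reply is that infant outcomes are probably not among the five primary outcomes. Aims 1A and 2A each list the same five maternal scales, so alpha 0.01 may not govern the infant tests. The infant hypothesis is 2B, so the infant text under 2A may simply be misplaced, and one sentence would settle it. The covariate bias is conditional, and nothing shows that PREPP changes weaning, return to work or support. The detectable effects borrow r from Aim 1, use attrition that the plan calls worst case, and take one value per visit, whereas sleep data are to be handled as daily records with AR(1) correlation. The order of the two tests also reverses within the range of r shown. Finally, no passage permits reporting whichever test is significant.

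Much of this stands as a limit on the figures. They are illustrative, they do not show that one model always costs power, and the error rates apply only if the choice is left open. The plan does not name its five primary outcomes, which is why results at alpha 0.05 are also given.

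The reply does not remove the defects. The infant text under 2A cannot simply be ignored, because 2B takes its covariates from that section, and 2B still names no tested parameter. Nor does the conditional nature of the bias justify putting possible mediators in the main infant model of a plan that promises intention to treat.

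**Conclusion.** The concern holds, and the text is wrong as written rather than merely brief. Two incompatible models cover infant outcomes at 6 and 16 weeks, and both include covariates that, as time-varying quantities, take values after assignment. The Treatment coefficient may therefore not be the effect of assignment to PREPP. How far it departs cannot be computed from the documents, and it would not depart at all for a covariate that PREPP leaves unchanged.

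The model conflict has a calculable consequence under the stated assumptions. The two tests differ in what they can detect by an amount, and in a direction, that depends on an unknown correlation, and free choice between them roughly doubles the false-positive rate per outcome. The maternal mood analyses are not affected. The point must be fixed because a stated Aim 2 hypothesis has no unambiguous test.

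**What to change.** - **One model.** State the same infant model in both paragraphs and delete the conflicting sentence. Name the Treatment effect averaged over 6 and 16 weeks as the tested parameter, with the Treatment × Time interaction as secondary. The average matches the directional hypothesis of less fuss/cry and longer sleep bouts. Other choices are defensible, provided that one contrast is named in advance.
- **Covariates.** Limit the primary infant model to Treatment, Time and covariates fixed or measured before assignment, for example birth order, infant sex and maternal age. Use the Prenatal 1 MSPSS only if the plan states that it was completed before assignment.
- **Post-assignment variables.** Move weaning, solid foods, return to work and postpartum support to a labelled sensitivity or mediation analysis, and state which visit's support value is used.

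The cost is wording in the Statistical Analysis Plan; no new data are needed. The primary infant model may explain slightly less residual variance, by an amount the documents do not allow to be estimated.
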